#### *Secondary outcomes:*

1. To measure incidence of SA recurrent skin and soft tissue infections at 1, 6 and 12 months independently in patients who did and did not receive systemic antibiotic therapy. Separate logistic regressions will be performed (at each time point) to see if antibiotic therapy is associated with SSTI after adjusting for covariates.
2. In order to assess the trend of SSTI's over 1 year follow-up we will use the Cochran-Armitage test for trend to determine if there are more SSTI's in the following year for patients colonized (determined at baseline).

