Data Collection: At study enrollment, a detailed questionnaire will be administered to identify risk factors for *S. aureus* colonization, infection, and transmission. Clinical data will be collected as well to track clinical signs at the time of presentation (vital signs, body site of infection, size of abscess, presence of systemic symptoms, type of incision and drainage, antibiotic use, type of packing applied). In addition, colonization swabs from the nose, axilla, inguinal folds and wound isolate will be collected and transported to [name] laboratory at Washington University. Longitudinal study visits will be conducted at the SIU Pediatric Infectious Disease Clinic one month following enrollment for research purposes only by PI or by the research coordinator. At this visit, a follow-up questionnaire will be administered inquiring about new, recurrent, or relapsed infection. Colonization swabs will be obtained and transported to [name] laboratory. Also history of any household members with any recent SSTI will be asked. Follow-up phone calls will be administered at 3, 6 and 12 months after enrollment to ask about recurrent infections. If an interval infection did occur, we will collect data regarding whether the individual sought medical care (and if so, the location where medical care was sought), the date of infection, the body site of infection, the bacteria causing infection, if known, whether the individual required a drainage procedure, surgery, or hospitalization, and whether the participant received antibiotics, oral or intravenous. If the patient sought medical care, records from the hospital and/or provider's office will be obtained for verification. Again, question about any household member having an SSTI will be made. Throughout the longitudinal study, we will ask participants to contact us if they develop a SSTI. The participant will be directed to seek medical treatment from their primary healthcare provider.

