### Specific Aim 2:

#### *Primary outcome:*

To measure incidence of SA recurrent skin and soft tissue infections at 3 months in patients who did or did not receive systemic antibiotic therapy. A binary logistic regression will be performed to see if antibiotic therapy is associated with SSTI at 3 months after adjusting for covariates.

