### Potential limitations:

Recruitment success rate is estimated to be around 30% in order to collect the desired patient sample (50 patients) in a 1 year period; this is based on a prior study in which the same population was targeted [39]. We recognize the complexity of having patients come to clinic for research purposes only in follow up. SIU School of Medicine's Department of Pediatrics is providing funds to complete the study beyond the 12 month period. Patient reimbursement of a \$20 check will be given at the follow-up visit for study purposes, without any charges to medical insurance. In previous studies conducted by our team, we had had a high longitudinal retention rate when the same incentive was given [39, 40]. Specimens will be obtained by research personnel and the collection technique. The surface area swabbed and the pressure used will be standardized for all participants. We have validated the shipping procedures for specimen transport to our collaborators at Washington University. We would like to evaluate whether shipment of the swabs can be done in a timely manner and whether the length of time required for shipment impacts the ability to successfully recover microorganisms. Reaching participant for follow-up phone calls may be a challenge, especially at 6 and 12 months after study enrollment; thus, we will obtain multiple methods of contact for each participant. A source of bias that we will have is the variability in the treating physician's decision to administer antibiotics or not. Adjusting for possible confounding factors and covariates will be made but these factors will not play a role in the primary outcome which is *S. aureus* colonization.

**Conclusion:** The Research Seed Grant, RSG, is an important step in achieving my career goal of becoming an independent investigator at SIU and will offer me a tremendous opportunity to help our patient population. The goal of this project is to obtain preliminary data which will allow me to apply for future external funding to be able to recruit more patients and to show a statistical significance. Recurrent *S. aureus* SSTI have become a major source of morbidity in our pediatric population. Decreasing the number of recurrent SSTI will decrease ED and PCP clinic visits and will benefit our public health.

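### Separate logistic regressions of recurrence at 1, 6 and 12 months waste the follow-up of children lost before 12 months; one censored time-to-first-SSTI analysis would use it

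*Combined protocol and SAP*

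**What the plan says.** Specific Aim 2, Secondary outcomes, item 1 covers recurrence at 1, 6 and 12 months: "Separate logistic regressions will be performed (at each time point) to see if antibiotic therapy is associated with SSTI after adjusting for covariates". The Aim 2 primary outcome uses the same method at one time point: "A binary logistic regression will be performed to see if antibiotic therapy is associated with SSTI at 3 months".

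The Data Collection section sets the contacts. The first is a clinic visit: "Longitudinal study visits will be conducted at the SIU Pediatric Infectious Disease Clinic one month following enrollment". The rest are by telephone: "Follow-up phone calls will be administered at 3, 6 and 12 months after enrollment to ask about recurrent infections". For each interval infection the study records "the date of infection, the body site of infection, the bacteria causing infection, if known". Families are also asked to report between contacts: "Throughout the longitudinal study, we will ask participants to contact us if they develop a SSTI".

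Potential limitations foresees attrition: "Reaching participant for follow-up phone calls may be a challenge, especially at 6 and 12 months after study enrollment". The answers given are operational: several means of contact, a $20 payment at the follow-up visit, and high retention in the team's earlier studies, for which no figure is given.

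The plan states no loss rate, no rule for a child who is not reached and no censoring rule. It does not say whether recurrence at 6 or 12 months is cumulative or counted since the last contact. The only analysis across the whole year, the Cochran-Armitage trend test, concerns baseline colonization and not antibiotic therapy.

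**The concern.** A logistic regression at a fixed time can use a child only if the outcome at that time is known. With loss expected at the later contacts, there are two ways to run the 12-month model.

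- **Analyse only children reached at 12 months.** A child seen to be infection-free to 6 months and then lost contributes nothing, and precision falls.
- **Also keep children with a known earlier recurrence.** Lost children who had been infection-free are still missing, so events are over-represented and risk is overstated.

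The plan does not choose between these, so the choice could be made after the data are seen. The Innovation section presents the long follow-up as distinctive, and the Conclusion says the data will support an application for a larger study. A sound 12-month incidence is therefore one of the more useful things this pilot can produce.

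**Working it through.** **Inputs from the documents.** N = 50; recurrence 50% without antibiotics (time point not stated) and 12-20% with them; stated power 50-80% (Sample size); significance level 0.05 (Data Analysis Plan); contacts at 1, 3, 6 and 12 months (Data Collection).

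**Assumptions.** Two-sided test, 25:25 split unless noted, 50% taken as a 12-month risk, exponential recurrence times, loss of 0-40% by 12 months.

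**1. The plan's own power.** With n per group and mean risk p̄, power = Φ{[|p1 − p2|√n − 1.96√(2p̄(1 − p̄))] / √(p1(1 − p1) + p2(1 − p2))}. For 50% v 20% and n = 25: (0.3 × 5 − 1.96 × 0.6745)/0.6403 = 0.278, so power is 0.61. For 50% v 12.5-12% it is 0.84-0.85. Fisher's exact test gives 0.51 and 0.76-0.77. No variant tried meets both stated ends within 2 points. Since the test and split are not given, 50-80% is a plausible rounded range and not shown to be wrong.

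**2. Cost of analysing only children reached.** The same formula for 50% v 20%, with n = 25 × (1 − loss):

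| Loss | n per group | Power |
|---|---|---|
| 0% | 25 | 0.61 |
| 10% | 22.5 | 0.56 |
| 20% | 20 | 0.51 |
| 30% | 17.5 | 0.46 |
| 40% | 15 | 0.40 |

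**3. How much a time-to-event test recovers.** Two sets of simulations compare a chi-square test among children reached at 12 months with a log-rank test censored at last contact. Set A has hazard ratio 0.35 (50% v 1 − 0.5^0.35 = 21.5%) and an interval-based log-rank test. Set B has 50% v 20% and uses dates. Each power rests on 4000 or 6000 runs, so its standard error is at most √(0.25/4000) = 0.008.

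| Set | Loss by 12 months | Split | Children reached | Time-to-event | Gain (points) |
|---|---|---|---|---|---|
| A | none | 25:25 | 0.58 | 0.56 | −2 |
| A | 10% | 25:25 | 0.53 | 0.55 | 2 |
| A | 20% | 25:25 | 0.48 | 0.51 | 3 |
| A | 30% | 25:25 | 0.423 | 0.478 | 5.5 |
| A | 30% | 40:10 | 0.348 | 0.410 | 6.2 |
| A | 40% | 25:25 | 0.378 | 0.456 | 7.8 |
| A | 40% | 40:10 | 0.32 | 0.41 | 9 |
| B | none | 25:25 | 0.628 | 0.611 | −1.7 |
| B | 20% | 25:25 | 0.527 | 0.556 | 2.9 |
| B | 30% | 25:25 | 0.472 | 0.516 | 4.4 |
| B | 40% | 25:25 | 0.418 | 0.477 | 5.9 |
| B | 30%, all at the 12-month call | 25:25 | 0.476 | 0.566 | 9.0 |

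Rejection under the null in set A was 0.048-0.058.

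**4. Keeping known events.** Let lost children have their last contact at 1, 3 or 6 months with weights 0.2, 0.3 and 0.5. With a 12-month risk of 50%, risk by time t is 1 − 0.5^(t/12): 0.056, 0.159 and 0.293. The share of lost children with a known event is 0.2 × 0.056 + 0.3 × 0.159 + 0.5 × 0.293 = 0.205. With loss L, apparent risk = [0.5(1 − L) + 0.205L] / [(1 − L) + 0.205L].

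- L = 20%: 0.441/0.841 = 52.4%
- L = 30%: 0.412/0.762 = 54.0%
- L = 40%: 0.382/0.682 = 56.0%

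With no true effect and 20% v 40% loss, the odds are 0.441/0.400 = 1.103 and 0.382/0.300 = 1.274, an odds ratio of 0.87. At 10% v 20% loss it is 1.046/1.103 = 0.95.

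**5. When uneven loss biases the comparison.** No true effect, 35% risk in both groups (assumed):

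| Mechanism | Spurious difference, logistic-type analysis | Spurious difference, censored analysis |
|---|---|---|
| 40% v 15% loss unrelated to recurrence, children reached only | 0.00 | 0.00 |
| Same loss, known events kept | 0.03 (0.392 v 0.362) | 0.00 |
| Recurrence-free untreated children lost more often, depending on observed history | 0.028 | 0.001 |
| Loss depends on recurrence since last contact | 0.056 | 0.033 |

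**The case against.** The plan nowhere says that unreached children are dropped. A child missed at 6 months may be reached at 12 and give the date of an earlier infection, families may report infections themselves, and records are obtained when care was sought. Retention in earlier studies is described as high. The power gain is small, rests on assumed loss, and leaves the comparison underpowered. The simulations use unadjusted tests, whereas the plan specifies adjusted models. Separate time points are a legitimate way to show an effect that may wane, and the trials cited in the protocol report differences in new lesions at 10 and 30 days. These are secondary outcomes of a 50-patient pilot.

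Most of this stands and limits the point. It does not remove it: the plan itself expects trouble at 6 and 12 months, and more ways of making contact do not say how to analyse a child who is still not reached. A waning effect can be shown with incidence by time point and a check across intervals.

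Three stronger readings are tempting, and the documents do not support them.

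- **The plan has a rule that drops unreached children.** It has none. Omission is what a logistic model does by default when the outcome is missing. The 1-month contact is also a clinic visit, not a call.
- **Uneven loss by itself biases the result.** Among children reached it does not (first row of step 5). Bias needs loss related to recurrence, or selective keeping of known events.
- **Nested outcomes are tested as if independent.** The plan does not say that the outcomes are cumulative, and separate regressions do not assume independence between time points.

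**Conclusion.** The point holds in a limited form. For an outcome whose dates are collected and whose later contacts are expected to be hard to complete, separate fixed-time regressions either discard observed infection-free time or, if known events are kept, overstate risk.

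The size is modest. The power gain is about 2-9 points at 10-40% loss and nil with complete follow-up; the 2 points at 10% are close to simulation error. The overstatement is 2-6 points on a true 50% at 20-40% loss, and arises only if known events are kept while lost infection-free children are not. Ignoring dates costs almost nothing when nobody is lost; the cost comes from attrition.

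The loss rates, group split, exponential timing, the 35% null risk and the reading of 50% as a 12-month figure are assumptions. The change is worth making, but the study does not depend on it.

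**What to change.** Keep the 3-month logistic regression as the Aim 2 primary. It shares the weakness in principle, so state how a child not reached at 3 months is handled.

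Replace the separate 1-, 6- and 12-month regressions with one analysis of time to first SSTI over 12 months:

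- a discrete-time complementary log-log model on the intervals 0-1, 1-3, 3-6 and 6-12 months, adjusted for the same covariates as planned;
- censoring at the last completed contact, applied alike to all children, with a sensitivity analysis for infections that families volunteer after that contact;
- Kaplan-Meier cumulative incidence with 95% CI by group at 1, 6 and 12 months;
- a descriptive check of whether the antibiotic effect changes across intervals.

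Recorded dates place an infection in its interval, which matters when a contact was missed. Beyond that only the contact window is needed, so imprecise recall does little harm.

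**Cost.** SAP wording, a file with one row per child per interval, and slightly more programming; no new data. The model assumes a proportional effect across intervals and non-informative loss. The adjusted comparison at each separate time point is given up, since the Kaplan-Meier estimates are unadjusted. Bias is reduced but not removed when loss depends on unobserved recurrence (0.056 to 0.033 in step 5). Confounding by physician-chosen treatment is addressed no further than the planned covariates allow.

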### Specific Aim 3:

#### *Primary outcome:*

To measure *S. aureus* antibiotic resistance in patients who did and did not receive systemic antibiotics, we will use a chi-squared test of independence to compare antibiotic resistance between patients who did and did not receive antibiotic therapy.

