Microbiology: Colonization swabs will be obtained at enrollment and at the 1 month follow-up visit by the PI or the research coordinator from the nose, axilla and inguinal folds. Four swabs will be used for each participant (1 each for both nostrils, both axillae, and both sides of the groin and the abscess site). Specimens will be collected with Copan E-swab™ Collection and Transport System to evaluate *S. aureus* colonization. This is a liquid-based multipurpose collection and transport system that maintains viability of aerobic, anaerobic and fastidious bacteria for 48 hours at room and refrigerator temperature. The research coordinator and I have successfully completed training for Shipping Infectious Materials and Biological Substances with SIU School of Medicine. Specimens will be shipped to Washington University in St. Louis, to the laboratory of [name] for microbiologic studies. If wound isolates from initial infection and a recurrence are available, they will be requested at the microbiology laboratory at SJH or MMC. After arrival, specimens will be incubated overnight in tryptic soy broth with 6.5% NaCl at 35°C. A sample of the broth will be plated to mannitol salt agar and incubated for 24-48 hours. Following confirmatory testing for *S. aureus* [37], susceptibility testing for cefoxitin (a surrogate for methicillin resistance) and 9 other antibiotics will be determined by Kirby-Bauer disk diffusion, in accordance with published guidelines [37]. Inducible clindamycin resistance will be tested [38]. All isolates will be stored in glycerol at -20°C.

Sample size: This is a pilot study to determine the feasibility of recruiting patients as described, having them return for 1 follow-up visit, and collaborating with Washington University for future

investigations. Our goal is to get preliminary data. According to available billing records (ICD-9 codes), since 2010, there has been in average 130 pediatric visits per month at SJH, MMC ED and Express Cares secondary to SSTI. Our goal is to recruit 50 patients in 12 months, which means that we will need about a 30% success rate for recruitment (**Figure 3**). A sample size estimate was performed to evaluate the power in the study. Considering an incidence of recurrent SSTI of 50% in patients who did not receive antibiotic therapy, a 60-75% percent reduction of recurrent SSTI (12-20% incidence) can be shown with 50-80% power.

[figure not shown]

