### Data Analysis Plan

Data on *S. aureus* identification will be collected from Washington University School of Medicine and recorded, along with questionnaire and clinical variables, on a data collection form by the principal investigator and research coordinator and then transferred to an excel spreadsheet for statistical analysis. Statistical Package for the Social Sciences (SPSS), version 20, will be used for data analysis.

Descriptive Statistics will be computed for all study variables. Continuous variables will be described with measures of central tendency (mean, median) and dispersion (range, standard deviation). Categorical variables will be summarized as frequencies and percentages.

We will calculate the frequencies/percentages for patient demographics, clinical characteristics, baseline questionnaire, follow-up questionnaires, and *S. aureus* colonization (nose, axilla, and inguinal folds) for each group: 1) Systemic antibiotic therapy 2) No systemic antibiotic therapy. Characteristics will be compared using independent t-tests for continuous variables and Chi-squared tests of independence for categorical variables. Significance will be assumed when  $p < 0.05$  or the 95% confidence interval.

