**Figure 3: Monthly Study Accrual Rates**

### Specific Aim 1:

#### Primary outcome:

To determine *overall* colonization status in children presenting with *S. aureus* abscesses who do and do not receive systemic antibiotic therapy at two time points (baseline and 1 month); a hierarchical logistic regression model will be used with colonization status as the outcome. Follow-up tests will be utilized when necessary.

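### Aim 3 compares resistance between physician-selected groups with an unadjusted chi-squared test that names no visit and makes no use of enrollment resistance

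*Combined protocol and SAP*

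**What the plan says.** The Specific Aim 3 text contains one analysis: "we will use a chi-squared test of independence to compare antibiotic resistance between patients who did and did not receive antibiotic therapy". It names no visit, isolate, drug, covariate or baseline term.

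Several sets of results could enter that test. The Data Collection paragraph says that at enrollment "colonization swabs from the nose, axilla, inguinal folds and wound isolate will be collected". The Microbiology paragraph says "Colonization swabs will be obtained at enrollment and at the 1 month follow-up visit", and adds "If wound isolates from initial infection and a recurrence are available, they will be requested at the microbiology laboratory". It also plans "susceptibility testing for cefoxitin (a surrogate for methicillin resistance) and 9 other antibiotics".

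The other two aims are more specific. Aim 1 looks at colonization "at two time points (baseline and 1 month); a hierarchical logistic regression model will be used with colonization status as the outcome". For Aim 2, "A binary logistic regression will be performed to see if antibiotic therapy is associated with SSTI at 3 months after adjusting for covariates".

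The Data Analysis Plan promises descriptive summaries of every study variable. Its list of what is summarised and compared by treatment group begins "We will calculate the frequencies/percentages for patient demographics, clinical characteristics, baseline questionnaire, follow-up questionnaires, and" and ends with *S. aureus* colonization by site. Resistance is not in that list. The Potential limitations section calls the physician's choice to give antibiotics a source of bias. It promises covariate adjustment in general terms, exempting only colonization.

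**The concern.** Aim 3 asks whether resistance differs between children who did and did not get systemic antibiotics. Those groups are not randomized, so resistance at enrollment need not be balanced. A test that ignores enrollment resistance can go wrong in two ways:

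- **1-month isolates compared.** An enrollment difference persists to 1 month and looks like an effect of the antibiotic. An opposite difference can hide new resistance.
- **Enrollment isolates compared or pooled in.** The test counts resistance that was there before the index antibiotic was given.

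The Conclusion says the purpose is preliminary data for a further funding application. The stated Aim 3 test would not show whether the result it passes on reflects resistance already present or resistance that emerged after treatment.

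**Working it through.** **Inputs from the documents.** The target is 50 patients (Sample size) and significance is at p < 0.05 (Data Analysis Plan). No resistance rate or group split is given, and Aim 3 has no power figure to reproduce.

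**Assumptions.** The test is two-sided and all 50 children are classifiable at both visits. Splits, treated:untreated, are 25:25, 40:10, 45:5 and 47:3. The last is near the almost 95% prescribing rate that the Management section cites from another hospital (0.95 × 50 = 47.5). A child resistant at enrollment is resistant at 1 month with probability 0.80 (persistence); a child not resistant becomes so with probability 0.05 (acquisition). Both are the same in each group, so the antibiotic has no effect.

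**Step 1: expected 1-month resistance.** With enrollment resistance *q*, it is *q* × 0.80 + (1 − *q*) × 0.05.

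- Treated, *q* = 0.60: 0.48 + 0.02 = 0.50.
- Untreated, *q* = 0.40: 0.32 + 0.03 = 0.35.

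A 20-point enrollment gap leaves a 15-point gap at 1 month with no drug effect.

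**Step 2: how often the planned test rejects.** With *a* of *n₁* treated and *b* of *n₂* untreated resistant, *s* = *a* + *b* and *N* = *n₁* + *n₂*, the statistic is X² = N[a(n₂ − b) − b(n₁ − a)]² / [n₁n₂s(N − s)]. The binomial probabilities of all tables with X² > 3.841 are summed.

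| No antibiotic effect | 25:25 | 40:10 | 45:5 | 47:3 |
|---|---|---|---|---|
| Chi-square, enrollment 60% v 40% | 21.6% | 13.9% | 9.4% | 3.9% |
| Chi-square, enrollment 55% v 45% | 10.0% | 7.2% | 5.9% | 2.6% |
| Chi-square, no imbalance (1-month 42.5% in both) | 6.2% | 5.3% | 4.8% | 3.7% |
| Mantel-Haenszel stratified by enrollment resistance, 60% v 40% | 4.5% | 4.3% | 5.2% | 6.9% |

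The Mantel-Haenszel row is simulated. With persistence varied from 60% to 90% at 60% v 40%, chi-square rejects in roughly 14 to 26%, 8 to 17%, 4 to 11% and 1.5 to 8.5% across the four splits.

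**Step 3: fewer analysable children.** With 30 instead of 50 (an assumption), the 60% v 40% case gives 12.5% at 15:15, 9.8% at 24:6 and 3.9% at 27:3.

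**Step 4: enrollment isolates compared.** At 60% v 40% the test rejects in 33.6%, 22.0%, 13.8% and 12.7%, for resistance the index antibiotic could not have caused.

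**Step 5: masking.** Let enrollment resistance be 40% treated v 60% untreated, acquisition 30% v 5%, and persistence 80%. One-month resistance is 0.4 × 0.80 + 0.6 × 0.30 = 0.50 v 0.6 × 0.80 + 0.4 × 0.05 = 0.50. The sixfold difference in acquisition disappears from the crude comparison. Chi-square rejects in 6.5%, 5.5%, 5.1% and 3.0%; a stratified exact mid-p test in 16.6%, 7.1%, 4.0% and 3.3%.

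**Step 6: price of stratifying when it was not needed.** With 50% enrollment resistance in both groups and acquisition 30% v 5%, power is 17.3%, 11.8%, 8.1% and 6.3% for chi-square, and 18.7%, 8.8%, 4.5% and 3.2% for the mid-p test.

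The mid-p figures depend on the version. Doubling the smaller tail is more conservative: with no effect and 60% v 40% it rejects in 3.4%, 2.2%, 1.9% and 1.3%, against 4.4%, 3.5%, 3.0% and 3.0% when tables no more probable than the observed one are summed.

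**The case against.** Several points on the other side stand, and they limit the reach of this concern.

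- **Text not supplied.** The pages before the Significance section were not available. They may state the aims, and could name the visit for Aim 3. The point therefore rests on the analysis text as supplied.
- **Partial cover elsewhere.** Descriptive statistics are promised for all variables, so resistance will be described in some form. The general adjustment sentence may be meant to reach Aim 3. But no by-group baseline table of resistance is specified, no Aim 3 model is named, and a chi-squared test of independence takes no covariates.
- **Exclusion criteria.** Children with anti-staphylococcal therapy or hospitalization in the prior 14 days, or decolonization measures in the last month, are excluded. This reduces recent selective pressure but does not guarantee balance.
- **Imbalance is assumed.** Inflation is modest at 55% v 45% and absent at 47:3.
- **Enrollment-only comparison.** This is the least natural reading of the aim, so Step 4 shows what the wording permits, not what is likely.
- **Pilot status.** Statistical significance is deferred to a larger study, so a formal stratified test matters less than clear tabulation. Naming the visit and showing both visits needs no power.

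A reader might infer that the Aim 3 result will be biased, or that baseline resistance is not measured. The documents support neither. They do not say whether resistance influences prescribing, and enrollment isolates are to be collected and tested. Nor does it follow that a stratified test is always better: at 47:3 the large-sample version rejects more often under no effect (6.9%) than chi-square does (3.9%).

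**Conclusion.** The concern holds as a gap in the analysis plan. On the supplied text, Aim 3 has one unadjusted test between groups formed by physician choice, names no visit, and leaves unused an enrollment measurement the study already provides. It is the only one of the three aims whose primary analysis has neither two named time points nor covariate adjustment.

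The bias is possible, not shown, and its size is unknown. False rejection of about 22%, 14%, 9% and 4% across the four splits rests on a 60% v 40% enrollment imbalance, 80% persistence, 5% acquisition and complete data on 50 children. It is smaller with a 55% v 45% imbalance or fewer analysable children. The benefit of stratifying is clear near an even split and small or nil at very uneven ones. The change is worth making because it is cheap.

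**What to change.** In the Specific Aim 3 text:

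1. Name resistance at the 1-month visit as the outcome.
2. Compare the groups stratified by, or adjusted for, enrollment resistance to the same drug where numbers allow. Use a small-sample method if one group is small, and state which version.
3. Tabulate resistance by group at both visits, including susceptible-to-resistant change among children with *S. aureus* at both. State the denominators and how a child with no *S. aureus* isolate at a visit is classed.
4. Make that table the main Aim 3 result if the split is very uneven.
5. Describe the result as an association.

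The lead drug, and whether the endpoint is resistance among isolates or carriage of a resistant strain, are for the investigator to choose.

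**Cost.** Plan wording and a little more analysis work; no new samples or visits. If enrollment resistance is in fact balanced, stratifying loses some power at uneven splits: in the example at 40:10, from about 12% to about 9%. With about 50 children there is little room for further covariates.
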